11.6.2.3 Questionnaires

11.6.2.3.1 Urge-to-Smoke Questionnaire of Smoking Urges Brief

The total score and the two factors from the QSU-brief will be listed for all scheduled time points and summarized overall and by the two stratification factors (sex, CC nicotine level at Admission) for the PK populations, as specified in Section 11.1.1 "Stratified Presentation". The individual responses to all questions will be listed by product, study day, and assessment time points.

In addition line graphs will be produced for the total score and factors means (and 95% CI) over all timepoints.

The analysis of the subjective effects of smoking (the total score, and Factor-1 and Factor-2 from the QSU-brief) will be performed using the same mixed effects ANOVA adopted for the analysis of CO breath test described in Section 11.6.2.2.1 "Exhaled CO and COHb". The time points of the THS 2.2 assessment schedule will be considered in the analysis, and data at T₀+15min for NRT gum will be imputed as described in Section 11.1.5 "Handling of Dropouts or Missing Data (including outside the limits of quantification)".

A sensitivity analysis using bootstrap techniques, will also be conducted on the total and factors score of QSU-brief, as described in Section 11.6.3 "Supportive/Sensitivity Analysis".

The main comparison will be the mean difference over all timepoints. LS means for each product, the overall mean difference (THS 2.2 - CC or THS 2.2 - NRT gum as appropriate) and the mean differences at each time point will be presented in the tables as

Statistical Analysis Plan Final v 2.0 / 07 April 2014 Confidential
Page 51 of 73

a point and interval (95% CI) estimate. Figures of the LS mean difference and 95% CI at each time point will be produced.

The data will be presented in the below outputs:

TFL number	Title
TABLES	
15.2.4.12	Analysis of QSU-brief Questionnaire Factors and Total Score – PK
	Population
15.2.4.15	Descriptive Statistics of QSU-brief Questionnaire Factors and Total
	Score – PK Population
15.2.4.15.1	Descriptive Statistics of QSU-brief Questionnaire Factors and Total
	Score by Sex – PK Population
15.2.4.15.2	Descriptive Statistics of QSU-brief Questionnaire Factors and Total
	Score by Nicotine Level – PK Population
FIGURES	
15.1.2.10.1	QSU-brief Factors and Total Score Profiles Arithmetic Mean and 95% CI
	- Group-1 PK Population
15.1.2.10.2	QSU-brief Factors and Total Score Profiles Arithmetic Mean and 95% CI
	- Group-2 PK Population
15.1.2.11.1	QSU-brief Factors and Total Score Profiles Arithmetic Least Squares
	Mean Differences and 95% CI – Group-1 PK Population
15.1.2.11.2	QSU-brief Factors and Total Score Profiles Arithmetic Least Squares
	Mean Differences and 95% CI – Group-2 PK Population
LISTINGS	
15.3.6.11	Listing of QSU-brief Questionnaire Results – Safety Population

11.6.2.3.2 Modified Cigarette Evaluation Questionnaire

The MCEQ domain scores composed of the three multi-item subscales and two single items from the MCEQ will be listed and summarized overall and by the two stratification factors (sex, CC nicotine level at Admission) for the PK populations, as specified in Section 11.1.1 "Stratified Presentation". The individual responses to all questions will be listed.

A mixed effects ANOVA model will be used to estimate mean THS 2.2-CC differences of the MCEQ domain scores and variances, with a REML method, using heterogeneous compound symmetry covariance structure (**Brown and Prescott**, 1999). Subjects within sequence will be used as random effects and fixed effects are period, sequence, and product exposure.

Statistical Analysis Plan Final v 2.0 / 07 April 2014 Confidential
Page 52 of 73

```
Proc mixed data=_data__ method=reml maxiter=200;
Class subject sequence product period;
Model response = sequence period product;
Random subject(sequence) / subject=subject type=csh;
Lsmean product / pdiff =control('CC/NRT') alpha=0.05 cl;
Run;
```

In case of model convergence issues, additional covariance structures will be investigated with the following order: heterogeneous autoregressive(type=arh), variance component (type=vc), and unspecified (type=un).

LS means for each product and the overall point and 95% interval estimate of the difference (THS 2.2 - CC) will be presented in the tables.

A sensitivity analysis using bootstrap techniques, will also be conducted on the MCEQ domain scores, as described in Section 11.6.3 "Supportive/Sensitivity Analysis".

The data will be presented in the below outputs:

TFL number	Title
TABLES	
15.2.4.16	Analysis of MCEQ Subscales – PK Population
15.2.4.17	Analysis of MCEQ Subscales by Bootstrapping Techniques - PK
	Population
15.2.4.18	Descriptive Statistics of MCEQ Subscales – PK Population
15.2.4.18.1	Descriptive Statistics of MCEQ Subscales by Sex – PK Population
15.2.4.18.2	Descriptive Statistics of MCEQ Subscales by Nicotine Level – PK
	Population
LISTINGS	
15.3.6.12	Listing of MCEQ Questionnaire Results – Safety Population

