The analysis of the exhaled CO during single use and log transformed blood COHb levels will be performed using a mixed effects ANOVA with a restricted maximum likelihood (REML) method to estimate mean differences and variances separately for THS 2.2 vs CC and THS 2.2 vs NRT gum, using heterogeneous compound symmetry covariance structure in order to allow unequal variances at the different timepoints (**Brown and Prescott, 1999**). Subjects nested within sequence will be used as a random effects and sequence, period, product and product*time point as fixed effect factors. The model will be evaluated including all of the different assessment timepoints, excluding the assessment prior to T₀, In addition, time point will be treated as a repeated measurement.

The SAS code to be used is shown below:

```
Proc mixed data=_data__ method=reml maxiter=200;
Class subject sequence product period;
Model log_COHb (or CO) = sequence period product time_point
product*time_point;
Random subject(sequence);
Repeated time_point / subject=subject*product type=csh;
Lsmean product / pdiff =control('CC/NRT') alpha=0.05 cl;
Lsmean product*time_point / pdiff alpha=0.05 cl;
Run;
```

In case of model convergence issues, this will be reported in the study report and additional covariance structures will be investigated with the following order: heterogeneous autoregressive(type=arh), variance component (type=vc), and unstructured (type=un).

For the analysis of CO breath test, the main comparison will be the difference over all time points. LS means for each product, the overall difference (THS 2.2 - CC or THS 2.2

Statistical Analysis Plan Final v 2.0 / 07 April 2014 Confidential Page 49 of 73

- NRT gum as appropriate) and the differences at each time point will be presented in the tables as a point and interval (95% CI) estimate. Figures of the LS mean difference and 95% CI at each time point will be produced.

For the COHb analysis, the main comparison will be the ratio over all time points. LS means for each product will be back-transformed by exponantiation and presented in tables together with the point and interval (95% CI) estimate of the overall ratio (THS 2.2:CC or THS 2.2: NRT gum as appropriate) and of the ratios at the different time points. Figures of the LS mean ratio and 95% CI at each time point will be produced.

TFL number	Title
TABLES	0.0000
15.2.4.7	Analysis of Blood COHb (%) – PK Population

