11.6.3 Supportive/Sensitivity Analysis

To support the interpretation of the PK analysis, the values of nicotine concentration greater than BLOQ before T_0 will be listed together with any PK parameters excluded from the analysis. Listing will be presented by PK parameter impact, sequence, period and study date.

To better understand the impact of the higher than expected T_0 values, an analysis of the PK parameters will be performed as described above, however the data for subjects with their T_0 value >5% of their C_{max} value will be excluded from the analysis.

Sensitivity analysis will be conducted on the C_{max} and $AUC_{(0-last)}$ endpoints for the Group-1 and Group-2 PK populations should there be 20% or more missing PK parameter values. This analysis is conducted on all the available PK parameters and subjects will be excluded from the analysis if the nicotine concentration T_0 value is >5% of their C_{max} value. The analysis will be conducted in the natural log scale using the same

Statistical Analysis Plan Final v 2.0 / 07 April 2014 Confidential

Page 53 of 73

mixed effects ANOVA model described in Section 11.6.2.3.2 "Modified Cigarette Evaluation Questionnaire". Point and 95% interval estimates of the ratios will be backtransformed by exponentiation and tabulated.

The same sensitivity analysis for C_{max} and $AUC_{(0-last)}$ endpoints will be conducted on t_{max} , in both Group-1 and Group-2 PK populations, supporting with THS 2.2 effect estimates on t_{max} adjusted for period, sequence, and subject within sequence.

In case any time information is imputed for the computation of PK parameters as described in Section 11.1.5 "Handling of Dropouts or Missing Data (including outside the limits of quantification)" in any PK population, the median t_{max} for THS 2.2 will be calculated following the imputation of missing time data by 0 sec and 30 sec. If the difference between the two median t_{max} is larger than 5%, a supportive analysis will be conducted by repeating the analyses described in Section 11.6.1 "Primary Analyses" and 11.6.2 "Pharmacokinetics" on the t_{max} , AUC_(0-last), and AUC_(0-t) endpoints estimated by means of the imputation of missing time by 0 sec.

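### The MCEQ mixed-model code gives every subject its own between-subject variance; if that fit is accepted, its intervals, and those of the PK sensitivity model that reuses it, are too narrow

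*SAP*

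**What the plan says.** For the MCEQ domain scores, the prose of SAP 11.6.2.3.2 describes a REML mixed model: "Subjects within sequence will be used as random effects and fixed effects are period, sequence, and product exposure". It adds that the model is fitted "using heterogeneous compound symmetry covariance structure". The code has the fixed part "Model response = sequence period product" and the random part "Random subject(sequence) / subject=subject type=csh". It has no REPEATED statement. If there are convergence issues, "additional covariance structures will be investigated with the following order: heterogeneous autoregressive(type=arh), variance component (type=vc), and unspecified (type=un").

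SAP 11.6.3 sends the PK sensitivity analysis of Cmax and AUC(0-last), in both groups, to the same "mixed effects ANOVA model described in Section 11.6.2.3.2", and then applies the same analysis to tmax. It is triggered when 20% or more of the PK parameter values are missing, and it uses all available values, so subjects with only one period stay in.

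Protocol 12.5.3 specifies subjects within sequence as random effects with period, sequence and product fixed, and Protocol 12.6.3 applies the same terms to MCEQ. SAP section 9, which lists the departures from the protocol, does not mention a different random structure.

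The repeated-measures code in SAP 11.6.2.2.1 is built differently. Its random term ("Random subject(sequence", closed without options) is plain, and the CSH structure sits on the time points: "Repeated time_point / subject=subject*product type=csh".

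**The concern.** In PROC MIXED, SUBJECT= on the RANDOM statement gives every subject an identical G block with one row per level of the random effect. Here the effect is itself subject(sequence), so the block has one row per subject, and TYPE=CSH gives each row its own variance. Each subject loads only on its own row. The result is a separate between-subject variance for every subject, each estimated from at most two observations, where the text calls for one common variance.

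This is the planned analysis of the MCEQ secondary objective (Table 15.2.4.16), which reports product LS means and the 95% interval of the THS 2.2-CC difference. It is also the stated sensitivity model for Cmax, AUC(0-last) and tmax. At stake is whether those intervals have the precision they claim, especially with missing periods, the situation for which the 11.6.3 analysis exists.

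**Working it through.** The documents give no figure that depends on this code, so there is none to reproduce.

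**Inputs.** Group-1 has 22 + 22 = 44 subjects and Group-2 has 9 + 9 = 18 (Protocol 4.1). The between-subject variance is not in the documents, so the intraclass correlation (ICC, between-subject variance over total variance) is an assumption, run from 0.3 to 0.9. Residual variance was set to 1. The ratios and coverages below do not depend on the measurement scale, so the planned CVs are not needed.

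**Parameter count.** Group-1: 44 variances + 1 correlation + 1 residual = 46 covariance parameters for 44 x 2 = 88 observations. Group-2: 18 + 1 + 1 = 20 for 36. No subject loads on two rows of the block, so the correlation never enters the likelihood. ARH also gives each row its own variance. UN would need 44 x 45 / 2 = 990 G parameters. Only VC gives the single variance described in the text.

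**Why the standard error shrinks.** The coded model gives subject i the covariance s_i² J + s² I. The described model gives s_B² J + s² I. With complete pairs and equal sequences, the product difference uses only within-subject differences, and its variance is 2s²/n in both models. The estimate is therefore the same, and only the estimate of s² differs. A subject whose mean lies close to the fitted mean gets s_i² = 0, and that small deviation then counts as evidence for a small s². A subject far from the fit is absorbed by a large s_i² and does not balance it. In the simulations 24-50% of the subject variances went to zero, and s² averaged 0.74-0.87 of its true value. At ICC 0.3, sqrt(2 x 0.741 / 44) = 0.184, against a true sqrt(2 x 1 / 44) = 0.213.

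**Simulation.** REML was fitted to 1000 simulated 2x2 crossovers per setting, with normal errors and values deleted at random, using (a) one variance per subject, bounded at zero, and (b) one common subject variance. Intervals are t-based with N - rank[X Z] degrees of freedom in both. Group-1 results, where SE ratio is (a) over (b):

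| ICC | Missing | SE ratio | Coverage (a) | Coverage (b) |
|---|---|---|---|---|
| 0.3 | 0% | 0.865 | 90.0% | 93.9% |
| 0.5 | 0% | 0.882 | 92.2% | 94.8% |
| 0.7 | 0% | 0.902 | 93.3% | 95.7% |
| 0.9 | 0% | 0.931 | 92.8% | 94.3% |
| 0.3 | 20% | 0.813 | 90.8% | 96.0% |
| 0.5 | 20% | 0.817 | 88.5% | 94.5% |
| 0.7 | 20% | 0.829 | 87.7% | 94.0% |
| 0.9 | 20% | 0.861 | 88.8% | 94.1% |
| 0.3 | 30% | 0.785 | 87.7% | 96.1% |
| 0.5 | 30% | 0.784 | 85.9% | 94.7% |
| 0.7 | 30% | 0.790 | 88.7% | 95.4% |
| 0.9 | 30% | 0.824 | 89.4% | 94.2% |

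Subtracting the ratios from 1 gives standard errors 7-14% too small with complete pairs, 14-19% with 20% missing and 18-22% with 30% missing. With missing periods the estimate itself also becomes slightly more variable. At ICC 0.5 and 20% missing its empirical SD is 0.262 under (a) against 0.256 under (b), while the mean reported SE is 0.203 against 0.249.

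Group-2 (n = 18) with 20% missing, at ICC 0.5 and 0.8: SE ratio 0.81-0.83, coverage about 90%.

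Further Group-1 simulations gave coverage of about 55-77% for the product LS-mean intervals under (a). Where the single-variance comparison was run, it covered 94-95%.

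**Limits.** At ICC 0.9 the optimiser flagged full convergence in only 66-74% of Group-1 fits, so those rows are less exact. A separate set of 400 complete-pair trials per setting gave the same SE ratios (0.86-0.93) but coverage of 92-95%, so the SE ratio is the steadier measure.

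**The case against.** **The fallback list may rescue the analysis.** An unidentified correlation and many variances at zero could well produce a convergence or Hessian problem, and VC, which is on the list, is the right model. This stands in part: how often a CSH or ARH fit would be reported is unknown, because SAS was not run. But the SAP does not say what counts as a convergence issue, so a fit that converges with a warning could be reported. ARH, which has the same defect, is tried before VC.

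**A bootstrap is planned.** SAP 11.6.3 requires a percentile bootstrap of the MCEQ scores (2000 samples, Table 15.2.4.17). With complete pairs the point estimate does not depend on the variance structure, so that interval does not inherit the faulty standard error. It is a partial independent check. It is a sensitivity result, however, and leaves Table 15.2.4.16 as it is.

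**The consequences are limited.** The MCEQ objective is descriptive, SAP 5.4.1 lists no MCEQ hypothesis, and SAP 11.1.7 makes no claims from individual tests. The PK use needs 20% missing values, while the sample size allows for at most 10% drop-out. All of this stands and bounds the weight of the point. For a descriptive objective, though, the interval is the result.

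**Stronger readings.** A reader might infer that the reported intervals will be too narrow whatever happens. The documents do not support that, since a fit that falls through to VC is sound. Nor do they support extending the point to the primary result. SAP 11.6.1 uses fixed-effects PROC GLM on subjects with both products, and the success criterion in 5.4.2 rests on that analysis. The CO, COHb and QSU-brief models use the plain random term. A reader might also suppose that CSH was intended to allow unequal variances by product. The only purpose the SAP states for it, in 11.6.2.2.1, is unequal variances across time points.

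**Conclusion.** The code in SAP 11.6.2.3.2 is wrong as written: it does not fit the model described in its own prose or in Protocol 12.5.3 and 12.6.3. If the CSH or ARH fit is accepted, the MCEQ difference is estimated correctly from complete pairs, but its standard error is about 7-14% too small and nominal 95% intervals cover about 90-93.5%. In the 11.6.3 sensitivity analysis, Group-1 standard errors are about 14-19% too small at 20% missing (coverage about 88-91%) and 18-22% too small at 30% missing (about 86-89%). Product LS-mean intervals are affected most, at about 55-77% coverage.

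These sizes rest on assumed ICCs of 0.3 to 0.9, normal errors, random missingness and a reading of PROC MIXED syntax without a SAS run. The direction of the SE bias was the same in every setting. It is a fault in a secondary and a conditional sensitivity analysis.

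**What to change.** In SAP 11.6.2.3.2, replace the RANDOM statement with `random subject(sequence);`, the form already used in 11.6.2.2.1, and remove the reference to heterogeneous compound symmetry from the prose. If product-specific variances are wanted, drop RANDOM and use `repeated product / subject=subject(sequence) type=csh;`, and say so in the text. Delete the ARH and UN fallbacks for the RANDOM statement. Make the same change to the model cited in 11.6.3 for Cmax, AUC(0-last) and tmax.

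The cost is one line of code and matching edits to the text. No data collection, sample size or primary analysis changes. With one common subject variance, simulated coverage of the product difference was 93.9-96.1% in every setting.

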11.6.3 Supportive/Sensitivity Analysis

To support the interpretation of the PK analysis, the values of nicotine concentration greater than BLOQ before T_0 will be listed together with any PK parameters excluded from the analysis. Listing will be presented by PK parameter impact, sequence, period and study date.

To better understand the impact of the higher than expected T_0 values, an analysis of the PK parameters will be performed as described above, however the data for subjects with their T_0 value >5% of their C_{max} value will be excluded from the analysis.

Sensitivity analysis will be conducted on the C_{max} and $AUC_{(0-last)}$ endpoints for the Group-1 and Group-2 PK populations should there be 20% or more missing PK parameter values. This analysis is conducted on all the available PK parameters and subjects will be excluded from the analysis if the nicotine concentration T_0 value is >5% of their C_{max} value. The analysis will be conducted in the natural log scale using the same

Statistical Analysis Plan Final v 2.0 / 07 April 2014 Confidential

Page 53 of 73

mixed effects ANOVA model described in Section 11.6.2.3.2 "Modified Cigarette Evaluation Questionnaire". Point and 95% interval estimates of the ratios will be backtransformed by exponentiation and tabulated.

The same sensitivity analysis for C_{max} and $AUC_{(0-last)}$ endpoints will be conducted on t_{max} , in both Group-1 and Group-2 PK populations, supporting with THS 2.2 effect estimates on t_{max} adjusted for period, sequence, and subject within sequence.

In case any time information is imputed for the computation of PK parameters as described in Section 11.1.5 "Handling of Dropouts or Missing Data (including outside the limits of quantification)" in any PK population, the median t_{max} for THS 2.2 will be calculated following the imputation of missing time data by 0 sec and 30 sec. If the difference between the two median t_{max} is larger than 5%, a supportive analysis will be conducted by repeating the analyses described in Section 11.6.1 "Primary Analyses" and 11.6.2 "Pharmacokinetics" on the t_{max} , AUC_(0-last), and AUC_(0-t) endpoints estimated by means of the imputation of missing time by 0 sec.

To evaluate the sensitivity to the distributional assumptions for the QSU-brief (see Section 11.6.2.3.1 "Urge-to-Smoke Questionnaire of Smoking Urges Brief") and MCEQ (see Section 11.6.2.3.2 "Modified Cigarette Evaluation Questionnaire") questionnaire scores, point and 95% interval estimates will also be assessed by means of the percentile bootstrap technique, using 2000 bootstrap samples which preserve the number of subjects per sequence.

The data will be presented in the below outputs:

TFL number	Title
TABLES	
15.2.4.3.1	Supportive Analysis of Pharmacokinetic Parameters of Nicotine Excluding Subjects with T ₀ Value >5% of Their C _{max} Value - PK
	Population
15.2.4.3.2	Analysis of Pharmacokinetic Parameters of Nicotine by Bootstrapping
	Techniques –PK Population
15.2.4.4	Analysis of Pharmacokinetic Parameters of Nicotine by Zero Sec
	Imputation –PK Population
15.2.4.14	Analysis of QSU-brief Questionnaire Factors and Total Score by
	Bootstrapping Techniques – PK Population
15.2.4.17	Analysis of MCEQ Subscales by Bootstrapping Techniques – PK
	Population

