12.5.3 Descriptive Analysis

Primary endpoints will be summarized as described in Section 12.1.3.

An analysis of variance (ANOVA) will be conducted on $AUC_{(0-last)}$ and C_{max} endpoints in the natural logarithmic scale. The model will include terms for sequence, subjects within sequence, period and product exposure as fixed effect factors. The results of this analysis for each of $AUC_{(0-last)}$ and C_{max} are presented in terms of adjusted geometric least square means and 95% CIs for the THS 2.2 :CC and THS 2.2:NRT gum ratios.

This approach is consistent with the guidelines in the European Medicines Agency's guidelines for bioequivalence investigations (EMA, 2008) and FDA's Center for Drug Evaluation and Research (FDA, 2001). Carry-over effect will not be tested, as it cannot be statistically distinguished from the interaction between treatment and period in a 2x2 crossover design (ICH E9, 1998).

A sensitivity analysis will be conducted should there be 20% or more missing PK parameter values, by repeating the above analyses using mixed effects ANOVA model in the natural log scale, with a restricted maximum likelihood method to estimate mean differences and

Confidentiality statement: Data and information contained in this document are considered to constitute trade secrets and confidential commercial information, and the legal protections provided to such trade secrets and confidential information are hereby claimed under the provisions of applicable law. No part of this document may be publicly disclosed without the written consent of Philip Morris Products S.A.

Philip Morris Products S.A.	Clinical Study Protocol	Confidential
ZRHR-PK-02-JP	Final 1.0 / 21 June 2013	Page 93 of 122

variances as suggested by FDA (FDA, 2001). Subjects within sequence will be used as random effects and fixed effects are period, sequence, and product exposure. To evaluate the sensitivity to the distributional assumptions, point and interval estimates will also be estimated by means of the percentile bootstrap technique, using 2000 bootstrap samples which preserve the number of subjects per sequence.

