3.1 Revision History

Version	Date of Revision	Revision
2.0	07 April 2014	 Due to the large number of T₀ nicotine concentrations that were higher than expected, the following changes to the statistical analyses were made: The primary analysis was changed to include all subjects irrespective of their T₀ concentrations (with respect to their C_{max}). The originally planned analysis (SAP v 1.0) became a supportive analysis. A typo in the formula for CYP2A6 activity was corrected
1.0	02 October 2013	Original SAP

Confidential

Philip Morris Products S.A. Statistical Analysis Plan

Protocol ZRHR-PK-02-JP Final v 2.0 / 07 April 2014 Page 7 of 73

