9 CHANGES FROM THE PROTOCOL SPECIFIED STATISTICAL ANALYSIS

Safety analyses will not be performed by product. Due to the study design it was determined that this presentation is not clear because of the product test at Admission and the selection of arbitrary time points for defining periods associated to the different study products may be misleading. In addition, the safety laboratory evaluations will only be collected prior to any product use and following the use of both products.

Shift tables for safety endpoints will not be produced for this study, because the relevant information will be provided in listings.

Statistical analysis for blood COHb (%) and exhaled CO (ppm) measurements and the QSU-brief questionnaire data will be performed including interaction terms for product and time point to enable LS means to be calculated at each time point in order to explore the pattern of the THS 2.2 effect over time. The main comparison between products will be the comparison over all time points.

Statistical Analysis Plan Final v 2.0 / 07 April 2014 Confidential
Page 29 of 73

Spirometry predicted values will not be standardized to the NHANES III predicted set as planned in the protocol. Predicted FEV₁ and FVC will be calculated according to the formula recommended by the Japanese Respiratory Society (Sasaki H, Nakamura M et al., 2001) for Japanese population.

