11.6 Planned Statistical Analyses

11.6.1 Primary Analyses

The primary parameters C_{max} and $AUC_{(0-last)}$ will be listed and summarized as described in Section 11.1 "General Considerations" and subsections .

Only subjects in the Group-1 PK population who provide evaluable data for both the THS 2.2 and CC products will be included in the following analyses.

The primary analysis of C_{max} and AUC_(0-last) will be performed on the natural log-transformed parameters using an analysis of variance (ANOVA) model with terms for sequence, subject nested within sequence, period and product as fixed effect factors (Senn, 2002, FDA, 2001, CHMP, 2010, and CHMP Appendix IV, 2011).

Carry-over effect will not be tested, as it cannot be statistically distinguished from the interaction between product and period in a 2x2 crossover design.

The SAS code to be used is shown below:

```
Proc glm data=_data_;
Class subject sequence product period;
Model log_pk = sequence subject(sequence) period product;
Lsmean product / pdiff =control('CC') alpha=0.05 cl;
Run;
```

where "log pk" is the the natural log-transformed PK parameter being analyzed.

Supportive analysis will be performed as described in Section 11.6.3 "Supportive/Sensitivity Analysis".

LS means for each product will be back-transformed by exponentiation and will be tabulated together with the ratio (THS 2.2 : CC) and 95% CI.

Statistical Analysis Plan Final v 2.0 / 07 April 2014 Confidential

Page 44 of 73

The geometric CV will also be presented as $\text{CV}(\%) = 100\sqrt{(e^{\text{MSE}}-1)}$, where MSE is the mean square error of the fitted model residual.

The data will be presented in the below outputs:

TFL number	Title	
TABLES		
15.2.3.1	Analysis of Primary Pharmacokinetic Parameters of Nicotine -	
	Group-1 PK Population	
15.2.3.2	Analysis of Primary Pharmacokinetic Parameters of Nicotine by Sex	
	and Nicotine Level - Group-1 PK Population	
15.2.4.5	Descriptive Statistics of Pharmacokinetic Parameters of Nicotine – PK	
	Population	
15.2.4.5.1	Descriptive Statistics of Pharmacokinetic Parameters of Nicotine by	
	Sex – PK Population	
15.2.4.5.2	Descriptive Statistics of Pharmacokinetic Parameters of Nicotine by	
	Nicotine Level – PK Population	
FIGURES		
15.1.1.1	Primary Pharmacokinetic Parameters of Nicotine – Group-1 PK	
	Population	
LISTINGS		
15.3.3.1	Listing of Pharmacokinetic Parameters of Nicotine - Safety	
	Population	
15.3.2.6	Individual Efficacy Response Data – PK Population	

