11.6.2.1.1 THS 2.2 vs CC

Only subjects in the Group-1 PK population will be included in the following analyses.

The secondary analysis of AUC_(0-∞), AUC_(0-t') and t_½ will be performed on the natural log-transformed parameters using the same ANOVA model as used for the primary analysis. (Section 11.6.1 "Primary Analyses"). Only subjects in the Group 1-PK population who provide evaluable data for both the THS 2.2 and CC products will be included in the analyses.

Statistical Analysis Plan Final v 2.0 / 07 April 2014 Confidential

Page 46 of 73

Supportive analysis will be performed as described in Section 11.6.3 "Supportive/Sensitivity Analysis" in order to evaluate the sensitivity of THS 2.2 effect estimates to methods used for missing data by means of a mixed model approach, should there be 20% or more missing parameter PK model.

The analysis of t_{max} will be performed by calculating the difference for each subject (THS 2.2 - CC) and obtaining the Hodges-Lehmann (Hodges and **Lehmann**, 1963) 95% CI estimates. The median t_{max} for each product and the median difference between the products along with the 95% CI will be presented in the tables. Supportive analysis will be performed as described in Section 11.6.3 "Supportive/Sensitivity Analysis" in order to evaluate the THS 2.2 effect estimates on t_{max} adjusted for period, sequence, and subject within sequence.

The data will be presented in the below outputs:

TFL	Title
number	
TABLES	
15.2.4.1	Analysis of Secondary Pharmacokinetic Parameters of Nicotine -
	Group-1 PK Population

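### The missing-data mixed model also drops subjects with pre-use nicotine (T0) above 5% of Cmax, so a difference from the primary analysis cannot be put down to missing data

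*SAP*

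**What the plan says.** - **Primary analysis.** SAP 3.1 records for version 2.0: "The primary analysis was changed to include all subjects irrespective of their" T0 concentrations. SAP 11.6.1 sets one data condition: "Only subjects in the Group-1 PK population who provide evaluable data for both the" THS 2.2 and CC products enter a fixed-effects ANOVA on the log scale.
- **T0 supportive analysis.** SAP 11.6.3 repeats the PK analysis without subjects whose T0 value is above 5% of their Cmax. Its output is Table 15.2.4.3.1, "Supportive Analysis of Pharmacokinetic Parameters of Nicotine Excluding Subjects with" T0 above that limit.
- **Conditional mixed model.** The next paragraph of 11.6.3 adds a sensitivity analysis of Cmax and AUC(0-last) for the Group-1 and Group-2 "PK populations should there be 20% or more missing PK parameter values". Of its data it says: "This analysis is conducted on all the available PK parameters and subjects will be excluded from the analysis if the nicotine concentration" at T0 is more than 5% of Cmax. The tmax analysis is then defined as the same sensitivity analysis.
- **Purpose.** SAP 11.6.2.1.1 refers to 11.6.3 for supportive analysis "in order to evaluate the sensitivity of THS 2.2 effect estimates to methods used for missing data by means of a mixed model approach", under the same 20% trigger.
- **Protocol.** Section 12.5.3 plans this check "by repeating the above analyses using mixed effects ANOVA model in the natural log scale" when 20% or more of the values are missing. It has no T0 exclusion.
- **Declared changes.** SAP section 9, "CHANGES FROM THE PROTOCOL SPECIFIED STATISTICAL ANALYSIS", does not mention a T0 exclusion in the mixed model.

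**The concern.** A sensitivity analysis for missing data is informative when it differs from the primary only in how missing data are treated. Here the primary uses complete pairs and ignores T0, while the check admits one-period subjects and applies a T0 rule. If the two results disagree, the reader cannot tell whether incomplete pairs or pre-use nicotine is responsible. If they agree, two effects may have cancelled.

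The T0 rule is not a marginal matter. SAP 3.1 gives a large number of unexpectedly high T0 concentrations as the reason for changing the primary analysis. The check would also run only when many values are missing, which is when a clear answer is most needed.

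**Working it through.** **1. The analyses side by side**

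| Analysis | Who enters | T0 rule | Model |
|---|---|---|---|
| Primary (SAP 3.1, 11.6.1) | complete pairs | none | fixed-effects ANOVA |
| T0 supportive (SAP 11.6.3) | complete pairs | T0 >5% of Cmax excluded | ANOVA, read from the reference back to the analyses above it |
| Conditional mixed model (SAP 11.6.3) | all available values | T0 >5% of Cmax excluded | REML, random subject |
| Same check in Protocol 12.5.3 | repeats the primary analyses | none | REML, random subject |

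The SAP mixed model differs from the primary in both who enters and the T0 rule. The protocol's version does not add a T0 rule.

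**2. What the planned comparison contains**

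On the log scale:

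(mixed, low T0) − primary = [(mixed, all T0) − primary] + [(mixed, low T0) − (mixed, all T0)]

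The first bracket is the missing-data effect and the second is the T0 effect. The SAP produces only their sum, because it plans no mixed model on all T0 values.

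**3. The T0 term can be non-zero with nothing missing (illustration)**

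Assume a share p of subjects is above the threshold and their log ratio differs by d. Neither value is in the documents. With complete data the primary estimates m + p·d and the low-T0 analysis estimates m, so the gap is p·d.

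- p = 0.25, d = 0.2: gap 0.05, and exp(0.05) = 1.051. A simulated 44-subject crossover with these values gave 1.051 for the primary, 0.999 for the mixed model as written, and 1.051 for the mixed model without the T0 rule.
- Across p of 0.10 to 0.40 at d = 0.2, p·d runs from 0.02 to 0.08, which is a ratio of 1.020 to 1.083.
- With d = 0 the gap still varies by chance. For Cmax the SD of a within-subject log difference is √(2·ln(1 + 0.36²)) = 0.494, using the 36% CV in SAP section 8. Keeping 33 of 44 subjects gives a gap SD of 0.494 × √(1/33 − 1/44) = 0.043. The simulation gave 0.045 with the T0 rule and 0.000 without it.
- With 20% of subjects missing one period (10% of values, so below the trigger), p = 0.25 and d = 0.2, the primary was 1.061, the mixed model without the T0 rule 1.060, and the mixed model as written 1.012.

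**4. When the check would run**

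The plan gives no figure for this analysis, so the counts start from the group sizes. The 44 reproduces: with SD 0.494 and target half-width ln 1.2 = 0.182, 39 evaluable subjects give probability 0.897, and 39/0.9 = 43.3, rounded up to 44.

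Assumption: the 20% is counted per endpoint and group over all randomized subjects. The SAP does not define the denominator.

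- **Group-1:** 44 × 2 = 88 values; 0.20 × 88 = 17.6, so 18 missing. If they fall in pairs, 9 subjects are lost, leaving 35 complete pairs and no one-period subjects. If they fall in 18 different subjects, 26 complete pairs and 18 one-period subjects remain.
- **Group-2:** 18 × 2 = 36 values; 0.20 × 36 = 7.2, so 8 missing. That leaves 14 pairs and no one-period subjects, or 10 pairs and 8 one-period subjects.

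The T0 clause removes further subjects from these remaining data.

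**The case against.** - **A matching comparator exists.** The T0-excluded analysis in Table 15.2.4.3.1 uses the same 5% rule, so setting the mixed model against it isolates missing-data handling. This is true if that table holds the ANOVA, but only within low-T0 subjects. It says nothing direct about the version 2.0 primary, and the SAP does not plan the comparison.
- **The sentence is not a contradiction.** It can be read as all available values among subjects who pass the T0 rule. That reading is fair, but the double difference from the primary remains under it.
- **The purpose is partly inferred.** The statement in 11.6.2.1.1 introduces AUC(0-∞), AUC(0-t') and t½ in Group-1, not Cmax and AUC(0-last). That is correct. The 20% missing-value trigger in both 11.6.3 and Protocol 12.5.3 still identifies the mixed model as a missing-data check.
- **tmax differs.** Its stated aim is adjustment for period, sequence and subject. It nevertheless inherits the T0 clause, which likewise mixes a change of subjects into that comparison.
- **The trigger may never be met.** Planned drop-out is at most 10%. In Group-1 that is 4.4 subjects, or at most 8.8 of 88 values (10%), below 20%. This limits the practical weight. The SAP does not say whether values removed under a T0 rule count as missing.
- **The denominator could be the PK population.** Nearly every member would then have Cmax in at least one period, so for Cmax the figures of 26 and 10 pairs are the relevant ends of the ranges.
- **The table point is soft.** Output shells are in a separate document. Still, 11.6.3 promises tabulated estimates, and none of its five listed titles names the mixed model.

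**Conclusion.** The concern holds. As written, the conditional mixed model changes both missing-data handling and T0 eligibility relative to the primary, so a difference between them cannot be attributed to missing data. It also departs from the protocol's version of the check without being declared in SAP section 9. This should be corrected, but it is confined to a conditional sensitivity analysis; the primary estimate and the ±20% precision criterion do not depend on it. No effect size is claimed, since the share of subjects above the threshold and their ratio are not in the documents. The values of p and d in the working are illustrations, and the trigger counts of 18 and 8 rest on the stated denominator assumption.

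**What to change.** In the missing-data paragraph of SAP 11.6.3, delete the clause that excludes subjects with T0 above 5% of Cmax. Run the mixed model on all available PK parameters in the PK populations, whatever the T0 value, so that it differs from the primary only in missing-data handling. The tmax analysis follows without its own edit because it is defined as the same analysis.

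Keep the T0 exclusion as the separate supportive analysis in Table 15.2.4.3.1. If a mixed model under that exclusion is also wanted, add it as a separately labelled analysis with the T0-excluded ANOVA as its comparator. Add a mixed-model table to the 11.6.3 output list.

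The cost is one deleted clause and one added table title, with no new data.
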